6.4 Additional analyses

Primary outcomes will be further presented by adherence and indication groups (e.g. children for which pulse oximetry was indicated and was used, children for which pulse oximetry was indicated but was not used, etc.).

6.5 Harms

Safety of the interventions will be evaluated in terms of deaths and secondary hospitalisations that occurred throughout the course of the study. Deaths, secondary hospitalisations and both combined will be reported as counts and percentages. Summary statistics will be presented separately for each intervention as outlined in Section 4.3.

6.6 Statistical Software

Statistical analysis will be performed using one of the standard statistical packages such as R v4.0.3 or higher versions [13]. The software and the version used for performing the analysis will be stated in the final statistical report.

7 REFERENCES

7.1 SOPs, study-specific Documents

- A. TIMCI Data Management Plan.
- B. TIMCI Data Monitoring Committee Charter.

8 APPENDIX A

The age of the child is expressed differently for *young infants* (i.e. children up to 59 days) and for children between 60 days and 59 months (sometimes more simply referred to as “2-59 months”)

- ξ It is grouped in three categories ([1-6 days]³, [7-27 days], [28-59 days]) for young infants;
- ξ It is expressed in months for children from 60 days to 59 months.

Figure 1) Recommended standardised age disaggregation groups for data analysis by life stage [6].

Recommended age grouping	Disease burden and health risk*	Examples of key prevention and health promotion interventions	Living conditions and societal factors
Early neonates	0-6 days	A third of all neonatal deaths occur on the day of birth, and nearly 75% occur within the first week of life	Immediate breastfeeding; vaccination (eg, for BCG and hepatitis B) and screening for genetic, endocrine, and metabolic disorders at birth or within the first 24 h of life
Late neonates	7-27 days	The first 27 days of life (neonatal or newborn period) are the most crucial for survival; neonates accounted for 2.5 million deaths (47% of all deaths under the age of 5 years) in 2019; ¹¹ causes of death in this age group differ from those in early neonatal and post-neonatal infants and a large proportion is due to congenital anomalies	Ensure neonates have received vaccines at birth, check weight, assess for birth defects, and promote the continuation of exclusive breastfeeding
Post-neonatal infants	28-364 days	The first year of life after the neonatal phase is the second riskiest period for child survival; about 24% of all deaths under the age of 5, in 2019, occurred in this age group, ¹¹ with pneumonia, diarrhoea, and malaria as leading causes of death	Completion of common vaccines schedule (diphtheria, tetanus, pertussis, Haemophilus influenzae type b, hepatitis B, poliovirus, pneumococcal, rotavirus, measles-rubella, and two doses of seasonal influenza); ³² continuation of breastfeeding with weaning and introduction of complementary foods when appropriate; long-lasting insecticidal nets and intermittent preventive treatment for infants in malaria-endemic countries
Young children	1-4 years	This group has the greatest reductions in mortality of all age groups to date, but mortality in this group remains fairly high in many countries; environmental exposures during the first 3 years of life can affect a child's developmental trajectory and lead to an increased risk of physical and psychological illness, affecting health and wellbeing in later life ²⁷⁻²⁹	Diphtheria, tetanus, pertussis, and measles-rubella boosters and seasonal influenza vaccine; ³² completion of weaning; long-lasting insecticidal nets and seasonal malaria chemoprevention in malaria endemic countries; early childhood programmes; environmental and policy interventions (eg, clean water and sanitation, fluoridation, safe playgrounds, and appropriate car seats)

The age of the child is available in the TIMCI database with different levels of accuracy depending on the information primarily shared by the caregiver. It can be either calculated as number of days between date of consultation and date of birth or estimated by categories.

Calculated Age

The date of creation of the ODK form is considered to be the date of consultation. The date of birth can be entered with three different levels of accuracy:

- ξ **DD/MM/YYYY**
If the exact date of birth is known, the age in month is derived from the age in days through a division by 30.44 $age_{month} = \frac{age_{days}}{30.44}$
- ξ The age is converted to the corresponding categories for young infants to keep the age granularity necessary while avoiding being able to indirectly recalculate the date of birth from the date of consultation and age in days:

$$\begin{aligned}
 1 \leq if \ age_{days} < 7 & \quad [1 - 6d] \\
 \{ 7 \leq if \ age_{days} < 28 & \quad [7 - 27d] \\
 28 \leq if \ age_{days} < 60 & \quad [28 - 59d]
 \end{aligned}$$

- ξ **MM/YYYY and YYYY**

³ The first day of life (or day of birth) is an exclusion criterion for TIMCI.

When the date of birth is not exactly known with a day accuracy, the age can only be known within a range of maximum and minimum ages.

The following approach is used:

- Young infants: those children who have their minimal age (variable *a3-a3_a_6a* in the Day 0 ODK form) in the interval [1-59 days]
- Children from 60 days to 59 months: those children who have their minimal age (variable *a3-a3_a_6a* in the Day 0 ODK form) in the interval [60 days - 59 months]

When only the year of birth is known, it is attempted to reduce the possible age range by clarifying the season of the birth of the child:

- January - March
- April - June
- July - September
- October – December
- Unknown (code: 98), the age range remains the one determined by the year of birth and the date of consultation

Estimated age

If the caregiver is not able to provide any elements of the date of birth, an available alternative is to select the category corresponding to the estimated age of the child.

The available categories that are defined in the data collection tool are as follow:

- Under 1 year
 - Under 1 month
 - ξ Less than 1 day (first day of life) ⇒ children excluded from the study
 - ξ 1-6 days
 - ξ 7-28 days
 - 1 month
 - 2 months
 - 3 months
 - 4 months
 - 5 months
 - 6 months
 - 7 months
 - 8 months
 - 9 months
 - 10 months
 - 11 months
- From 1 to under 2 years
 - 1 year and 0-2 months (12-14 months)
 - 1 year and 3-5 months (15-17 months)
 - 1 year and 6-8 months (18-20 months)
 - 1 year and 9-11 months (21-23 months)
- From 2 to under 3 years
- From 3 to under 4 years
- From 4 to under 5 years

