6 ANALYSIS

Analyses will follow Consolidated Standards of Reporting Trials (CONSORT) guidelines [10] and will be performed and reported overall and by country.

Outcomes will be presented separately for young infants (<60 days) and older children (60 days-59 months), the malaria-related outcomes will be presented only on older children.

Results of interim analyses and DMC analyses will be presented overall in the open report and by intervention arm in the closed report.

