6.2.5 Pre-specified Subgroups Analysis

Subgroup analysis of the primary outcomes are planned to assess effect modifiers, specifically:

- ξ Age (under 2 months, 2 – 12 months, 13 – 59 months) – as recorded at Day0
- ξ Sex (male, female) – as recorded at Day0
- ξ Presentation with cough or difficulty breathing (yes, no) – as recorded at Day0
- ξ Diagnosis (severe, non-severe)
- ξ Referral (yes, no)
- ξ Antimicrobial drug prescription (yes, no). Antimicrobials are defined as antimalarials and antibiotics, according to the same definition used for the outcomes.
- ξ Stratification factors (location and facility type)

Effect modification will be assessed by incorporating an interaction between the time period and the potential effect modifier in the model, acknowledging that power will be low. Stratified model results will only be presented if the interaction term is significant, defined as p-value<0.2.

For interim analyses and DMC analyses, no subgroup analysis is planned.

² Urgency, as reported by the caregiver, was only collected in Tanzania. For India, urgent referrals will be defined based on the registry alone, as described for the primary analysis.

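### Where the day of birth is unknown, the SAP sets the age group on minimum possible age alone, so some children of 60 days or more are reported as young infants; separately, one recorded age category straddles the 12/13-month subgroup cut

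*SAP*

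**What the plan says.** SAP Appendix A has three routes to age. With an exact birth date, age is counted in days. With month and year, or year only, the SAP accepts that "the age can only be known within a range of maximum and minimum ages". If only the year is known, the form asks for the quarter of birth; if that is unknown too, "the age range remains the one determined by the year of birth and the date of consultation". For this second route, the young-infant label is defined by "Young infants: those children who have their minimal age", held in a variable "in the Day 0 ODK form) in the interval [1-59 days"], and the older label goes to those with the same variable "in the Day 0 ODK form) in the interval [60 days - 59 months"]. Maximum age plays no part, and a minimum age of 0 is not mentioned. With no element of the date, the research assistant picks an estimated category, one of which is "1 year and 0-2 months (12-14 months"). The minimum-age rule is not stated for this third route.

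The grouping is used in several places. SAP section 6 reports outcomes separately for the two groups and adds that "the malaria-related outcomes will be presented only on older children". SAP 4.2 treats oximetry in Tanzania as indicated for every young infant, and SAP 6.4 tabulates primary outcomes by indication and use. SAP 6.2.5 lists the subgroup "Age (under 2 months, 2 – 12 months, 13 – 59 months"). No sensitivity analysis in SAP 6.2.4 concerns the accuracy of age.

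**The concern.** Setting the group by one end of an interval gives an error with a direction. Every misplaced child on this route is an older infant counted as a young infant.

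Protocol 6.3 describes young infants as a small part of attendance with relatively high risk. If older infants carry lower risk, adding them dilutes the young-infant event rate, and a small group needs few additions for that to show. The same children drop out of the malaria outcomes, although SAP 6.1.4 counts febrile children from 60 days among those who should be tested in Tanzania. Some also enter the Tanzanian indication tables as children for whom oximetry was indicated.

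Two further gaps concern allocation. A child born in the current month, quarter or year has a latest possible birth date equal to the consultation date. The minimum age is then 0 unless the form floors it, and 0 lies in neither stated interval. And a child recorded as 12–14 months may belong on either side of the 12/13-month cut.

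**Working it through.** The plan gives no figure on this point to reproduce, so the check applies the rule as written.

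**Definitions.** Let c be the consultation date, and s and e the first and last day of the recorded birth month, quarter or year.

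- Minimum age = c − min(e, c); maximum age = c − s.
- Young infant if the minimum is 1 to 59 days; older child if it is 60 days or more (Appendix A).
- True young infant: 1 to 59 days. The day of birth is excluded (SAP 5.2, Appendix A footnote).

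**Single cases.**

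| Seen | Recorded birth | Range (days) | Example of a true age | Label |
|---|---|---|---|---|
| 15 June | April | 46–75 | 74 (born 2 April) | young infant |
| 20 May | January–March | 50–139 | 130 (born 10 January) | young infant |
| 10 February 2022 | 2021 | 41–405 | 401 (born 5 January 2021) | young infant |
| 15 June | June | 0–14 | 12 (born 3 June) | neither, if the form returns 0 |

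**Enumeration.** Every consultation day of 2022 (365) is crossed with every true age from 1 to 1825 days, equally weighted (an assumption). True young infants number 365 × 59 = 21,535 day-age cells at each precision. The share wrongly labelled is (older labelled young) / (older labelled young + true young labelled young).

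| Birth date known to | Form returns 0 | Form floors at 1 day | Oldest child labelled young infant |
|---|---|---|---|
| Month | 5,373 / (5,373 + 16,162) = 25% | 5,373 / (5,373 + 21,535) = 20% | 89 days |
| Quarter | 14,455 / (14,455 + 7,080) = 67% | 16,472 / (16,472 + 21,535) = 43% | 150 days |
| Year only | 19,765 / (19,765 + 1,770) = 92% | 66,430 / (66,430 + 21,535) = 76% | 423 days |

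No true young infant is labelled older in any row. If young infants attend at half the uniform density, the shares rise to 40%, 80% and 96% (returns 0) or 33%, 61% and 86% (floored).

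**Neither group.** If the form returns 0, the share of true young infants fitting neither interval is (21,535 − 16,162) / 21,535 = 25% (month), (21,535 − 7,080) / 21,535 = 67% (quarter) and (21,535 − 1,770) / 21,535 = 92% (year only). With a year-only date the unassigned group extends to 364 days of age. If the form floors at 1 day, it is empty.

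**Alternatives to the rule.**

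| Birth date known to | True young infants kept by midpoint rule | Midpoint-labelled young infants really 60 days or older | True young infants with whole range under 60 days |
|---|---|---|---|
| Month | 94% | 6.6% | 75% |
| Quarter | 81% | 20% | 33% |
| Year only | 24–25% | 25–26% | 8% |

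**The 12/13-month cut.** Of the estimated categories in Appendix A, only 12–14 months crosses it: 12 belongs below the cut, 13 and 14 above. A cut at 12 months falls between the categories 11 months and 12–14 months, and agrees with the boundary between 28–364 days and 1–4 years in the Appendix A figure.

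**The case against.** The form is not among the documents. Since the day of birth is excluded, the youngest eligible child is 1 day old, which is the lower bound of the stated interval; the form may well floor the minimum there. The SAP's rule then captures every true young infant, a defensible choice for a high-risk group. Classifying by midpoint would lose about 6%, 19% and 75–76% of true young infants at month, quarter and year-only precision. The main comparisons use all recruited children (SAP 6.1.2), and SAP 6.2.5 already concedes low subgroup power. All of this stands. It limits the size of the point and rules out the midpoint as the main rule, but the one-way error remains under either form behaviour.

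A reader might infer more than the documents support:

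- That many children are affected. The share of partial dates is not given, and the percentages are per partial-date record.
- That every child without an exact birth date is affected. The rule is not stated for the estimated-category route.
- That the youngest children certainly fall in neither group. This depends on an undocumented form value.
- That oximetry is wrongly counted as indicated for all misplaced Tanzanian children. Those with cough, breathing difficulty or a yellow or red classification are in the indicated group anyway (SAP 4.2). In India it is indicated for all.
- That the primary results are biased. Nothing suggests the error differs by arm.

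**Conclusion.** The point holds in a limited form. For month-and-year and year-only records, the Appendix A rule moves some children of 60 days or more into the young-infant group and none the other way. The wrongly labelled share is about 20–25%, 43–67% and 76–92% at month, quarter and year-only precision, assuming uniform ages and consultation dates; the spread reflects the unknown handling of a minimum age of 0. The number of children involved cannot be derived.

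The consequences reach the age-stratified outcomes, the malaria population, part of the Tanzanian indication tables and the under-2-months subgroup. The all-children primary comparisons, the sample size and alpha are unaffected. The 12/13-month problem is separate and smaller: one pick-list category has no stated side.

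**What to change.** 1. In Appendix A, make the lower interval include a minimum age of 0 for eligible children, and report counts by date precision (exact, month, quarter, year only, estimated). This closes the gap whatever the form returns. The floored shares (20%, 43%, 76%) then describe what remains.
2. In SAP 6.2.4, add a sensitivity analysis of the young-infant results and the under-2-months subgroup, restricted to children whose whole possible age range is under 60 days, exact dates included. Treat ranges that span 60 days as indeterminate in that check. Keep the present main rule rather than switching to the midpoint.
3. In SAP 6.2.5, use 2–11 and 12–59 months, with a note that this differs by one month from the label in protocol 6.4.2.

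The cost is SAP wording and a little more analysis. The check loses 25% of true young infants with month-only dates, 67% with quarter and 92% with year only. The SAP names only a minimum-age variable and coarsens some ages for privacy, so the sponsor should confirm that maximum age can be derived, if necessary before de-identification. The new cut is a small departure from the protocol's subgroup label, and it does not resolve year-only ranges, which can cross any boundary.
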